4.0 REGISTRATION PROCEDURES

Patients can be registered only after eligibility criteria are met. Patients must have signed informed consent. Patients are registered prior to any protocol treatment by faxing the registration page to [contact] and calling [contact]. The UW data managers will verify eligibility, assign a case number, dose level, and confirm the number of fractions per week.

Patients will be enrolled on the highest available dose level open to accrual. If the highest dose level has reached full accrual with insufficient follow-up for further dose-per-fraction escalation, accrual will take place at one dose level lower, if one exists.

Enrollment will be permanently closed when the maximum tolerated dose per fraction is reached or when the dose per fraction escalation is complete.

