5.2 Dose-per fraction escalation

Escalation to the next higher dose-per-fraction level (or the accrual of an additional 100 patients to the MTS) will only be allowed when there is at least 20 patient years of follow-up and at least 5 patients have been followed for at least 12 months. A rate of 20% grade 2 or higher late rectal toxicity per patient follow-up year will be considered dose limiting. Late toxicities will be scored > 90 days from completion of therapy. The statistical rationale and methodology for this dose-per-fraction escalation strategy is described in section 8.0. Of note, statistical fluctuations in measured toxicity rates could occasionally lead to an initial over- or underestimation of these rates. Therefore, cumulative toxicity rates will be updated every 6 months throughout the life of the protocol and will be utilized according to the rules stated above.

The expected accrual timetable, the proposed dose-per-fraction and total fraction levels, and patient accrual goals for this phase I/II trial are shown in Table 1 below.

Table 1: Fraction size dose escalation protocol

Level	Approx. Interval (mo)	Dose per Fx (Gy)	# Fxs	# pts	Treatments per week	Total dose (Gy)	Equiv. dose (Gy)
I	1-15	2.94	22	50*	3 ← 4 → 5	64.68	82.6
II	16 - 30	3.63	16	50	3 ← 4 → 5	58.08	85.1
III	31 - 45	4.3	12	50	3 ← 4 → 5	51.6	85.5

* See section 5.1 for exceptions. Patients are initially treated 3 or 4 times per week, with this treatment frequency subsequently increasing, decreasing or remaining the same based upon the number of acute toxicities observed, as described in Section 5.3.

All of the three above levels are predicted to be approximately isoeffective for late effects at BED_3 equals approximately 128 Gy₃. In other words, each of these dose-per-fraction levels would be predicted to produce about the same level of late toxicity, all other factors such as high dose rectal wall volume remaining constant. Furthermore, the above schemas are all predicted to produce the same late toxicity as the fractionation regimen successfully piloted by Kupelian and Mohan(23) of 2.5 Gy times 28 fractions.

An additional **100** patients may be accrued to the MTS if toxicities observed in the first patients at the level are within the limits specified in the standard escalation rules.

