5.3 Number of fractions per week and acute toxicities

Acute toxicities, as defined in section 5.6, will be assessed to determine the number of fractions at the given fraction size that can be delivered per week. The first 10 patients enrolled at each fraction size level will receive either 3 or 4 fx/week, depending upon how well tolerated previous fractionation levels and weekly treatment frequencies were tolerated. Acute toxicities will be reanalyzed and acted upon if necessary for subsequent groups of 10 patients. For toxicities observed within the first 10 patients at each hypofractionation level, $\geq 20\%$ acute grade 3 or higher GI or GU toxicity will constitute a threshold toxicity level and will dictate a decrease in frequency of treatment by one treatment per week for the next 10 patients to be treated at that hypofractionation level. If $> 20\%$ acute toxicity is also observed in this second group of 10 patients, treatment frequency will be further reduced by one treatment per week for all remaining patients in that hypofractionation level. If excess toxicity is not seen **after changing to a** lower treatment frequency, then all remaining patients in that hypofractionation level will continue to be treated at that frequency.

- If exactly 20% of patients within the first group of ten patients at any hypofractionation level experiences acute grade III or higher GI or GU toxicity, then the next ten patients at that hypofractionation level will remain at the same weekly frequency of treatment,

subject to the usual treatment frequency de-escalation if excess acute toxicities are observed.

- If < 20% of the first ten patients within the level experience this threshold toxicities, then the subsequent patients will be treated at the next higher treatment frequency sublevel, again subject to de-escalation if excess acute toxicities are observed.
- For an individual patient who develops acute toxicity at or above the Grade 3 level, that patient will be placed on treatment break for one week and treatments will then resume at the next lower treatment frequency. For example, if that patient was being treated 4 times per week at the time grade 3 or higher acute toxicities developed, he would subsequently be treated 3 times per week. A longer treatment break can also be prescribed if the treating physician feels that it is clinically indicated.

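### Section 5.3 orders both a decrease and no change in weekly frequency when exactly 2 of the first 10 patients have acute grade 3+ toxicity; separately, acute Grade 4 toxicity means resume in 5.3 and stop in 5.8.

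*Combined protocol and SAP*

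**What the plan says.** **Group rule.** Section 5.3 sets the weekly frequency from acute toxicity in successive groups of 10 patients at each level. For the first 10, the main paragraph sets the trigger at 20% or more (a greater-than-or-equal sign): this much "acute grade 3 or higher GI or GU toxicity will constitute a threshold toxicity level and will dictate a decrease in frequency", by one treatment per week for the next 10. For the second 10 the trigger is written as more than 20%: if that much "acute toxicity is also observed in this second group of 10 patients, treatment frequency will be further reduced by one treatment per week". If a decrease is not followed by excess toxicity, "then all remaining patients in that hypofractionation level will continue to be treated at that frequency".

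Two bullets follow on the first group. One opens with the condition "If exactly 20% of patients within the first group of ten patients at any hypofractionation level experiences acute grade III or higher GI or GU". The action it orders for that count is "then the next ten patients at that hypofractionation level will remain at the same weekly frequency of treatment". The other says that less than 20% moves later patients up one frequency step. The note to Table 1 in section 5.2 describes patients starting at 3 or 4 treatments per week, "with this treatment frequency subsequently increasing, decreasing or remaining the same based upon the number of acute toxicities observed". Under section 4.0, the coordinating centre's data managers "assign a case number, dose level, and confirm the number of fractions per week".

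**Individual rule.** For a patient whose acute toxicity is Grade 3 or worse, section 5.3 says "that patient will be placed on treatment break for one week and treatments will then resume at the next lower treatment frequency". The worked example that follows has the same Grade 3-or-higher scope. Section 5.8 lists the severe toxicities of section 5.6.3 among the reasons to stop study treatment, and 5.6.3 covers every Grade 4 and Grade 5 toxicity.

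**The concern.** The main paragraph and the first bullet share the endpoint, the ten patients assessed and the ten patients affected, yet they order different actions. In a group of 10, 20% is a whole number of patients, so the overlap can occur. Because frequency is confirmed centrally, sites would not drift apart. But the centre would have to choose between the rules after seeing the count, which a pre-specified decision rule is meant to prevent. A decrease can also carry forward to everyone still to be treated at the level.

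The second conflict concerns one patient's further irradiation. Acute Grade 4 is a defined category in section 5.6.1 and includes bleeding that needs transfusion and acute bladder obstruction. One section has such a patient restart after a week; another ends his study treatment. A safety instruction should have one answer.

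**Working it through.** The plan states no operating characteristics for the acute-toxicity rule, so there is no figure to reproduce.

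**1. First-group rules by count (n = 10, section 5.3)**

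| Patients with acute grade 3+ | Main paragraph | Bullets |
|---|---|---|
| 0 or 1 (under 20%) | – | increase |
| 2 (exactly 20%) | decrease by one | no change |
| 3 or more (over 20%) | decrease by one | – |

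Only the row for 2 has two entries, and they disagree. Nothing in 5.2, 5.3 or section 8 says which prevails.

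**2. Which trigger was probably meant.** The bullets deal with exactly 20% and with less than 20%, which leaves more than 20% for a decrease. The second-group trigger is more than 20%, worded as a repeat of the first. With 20% or more as the trigger, the exactly-20% bullet would have no case left to govern.

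**3. How often the count of 2 would arise.** The true acute grade 3+ rate p is not in the documents, so a range is assumed. With X ~ Binomial(10, p), P(X = 2) = 45 p²(1 − p)⁸. At p = 0.10 this is 45 × 0.01 × 0.4305 = 0.1937. At p = 0.01 it is 0.0042 and at p = 0.03 it is 0.0317. For higher rates:

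| p | P(X = 2) | P(decrease) if trigger is 2 or more | P(decrease) if trigger is 3 or more |
|---|---|---|---|
| 0.05 | 0.0746 | 0.0861 | 0.0115 |
| 0.10 | 0.1937 | 0.2639 | 0.0702 |
| 0.20 | 0.3020 | 0.6242 | 0.3222 |
| 0.30 | 0.2335 | 0.8507 | 0.6172 |

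The last two columns differ by P(X = 2), so they restate the same gap as a decision probability. If all three levels open with the same p and independent groups, the chance of meeting the count at least once is 1 − (1 − P(X = 2))³: 20.8% at p = 0.05, 47.6% at 0.10 and 66.0% at 0.20.

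**4. What a decrease changes.** Course length is the number of fractions (Table 1) divided by fractions per week. From a start of 4 per week down to 3:

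- Level I: 22/4 = 5.5 to 22/3 = 7.3 weeks
- Level II: 16/4 = 4.0 to 16/3 = 5.3 weeks
- Level III: 12/4 = 3.0 to 12/3 = 4.0 weeks

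This applies to the next 10 patients and, if the lower frequency is then tolerated, to all 50 − 10 = 40 remaining.

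**5. Individual rule by grade, for an event during radiotherapy**

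| Acute grade | Section 5.3 | Section 5.8 with 5.6.3 |
|---|---|---|
| 3 | break one week, resume at lower frequency | not listed as a stop |
| 4 | break one week, resume at lower frequency | stop |

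Section 5.3 makes no exception for Grade 4, and 5.8 and 5.6.3 make none for acute events. The documents support no rate for acute Grade 4 events, and none is assumed.

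**The case against.** The strongest reply is that the text resolves itself. The exactly-20% bullet addresses a single count, and a specific rule is normally read as overriding a general one. That reading probably matches the intent. It is still an inference: the protocol does not state it, and the main paragraph is worded as mandatory.

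The first conflict turns on one sign, and a misreading of the PDF cannot be wholly excluded. However, the text has a greater-than-or-equal sign in one sentence and a plain greater-than sign in the next, so they were read as different symbols.

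The Table 1 note is weak evidence of intent. It does not tie the unchanged outcome to the first group, and frequency can also stay put after a successful decrease. The argument in step 2 does not need it.

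The consequences are bounded, and this stands. Late-toxicity escalation, the precision of disease-free survival and the biomarker power are untouched. Under the no-change reading the next ten remain subject to de-escalation, and a patient with Grade 3 toxicity is still paused and slowed individually. The larger probabilities need assumed rates of 10% or more; at 1% to 5% the conflict arises at 0.4% to 7.5% of levels.

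On Grade 4, a clinician would probably let the stop rule win. Section 5.8 also allows stopping on the physician's judgement, and Grade 4 events are reported promptly to the study chair and the DSMB. Resumption by default is therefore unlikely, but the two instructions remain incompatible as written.

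**Conclusion.** Both contradictions hold as the text stands. At 2 of 10, section 5.3 orders a decrease and no change together, without precedence. The chance per level is 0.4% at a true acute grade 3+ rate of 1%, 7.5% at 5%, 19% at 10% and 30% at 20%, which is the plan's own threshold. These rates are assumptions, and the calculation treats patients as independent. The effect falls on weekly frequency for 10 to 40 patients at a level. Independently of any rate, a patient with acute Grade 4 toxicity during radiotherapy falls under both a resume rule and a stop rule. Neither conflict alters the dose-per-fraction decision. Both should be corrected because they are operative treatment rules that cannot both be followed.

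**What to change.** 1. In the main paragraph of 5.3, change the first-group trigger from 20% or more to more than 20%. Then 0 or 1 of 10 means increase, 2 means no change, and 3 or more means decrease. This agrees with both bullets and with the second-group rule.
2. In 5.3, limit the individual break-and-resume bullet and its worked example to Grade 3, and add that Grade 4 toxicity stops study treatment under 5.8.

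The cost is a short amendment: one sign, an edited bullet with its example, and one added sentence. It needs no extra patients or procedures.

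The same amendment could settle a neighbouring gap. A group decrease from a start of 3 per week, or a second decrease from 4, leads to 2 per week. Table 1 does not list that frequency, and 5.3 expressly allows it only for an individual patient.

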- At any hypofractionation level, a reduction in treatment frequency to two fractions per week will be allowed for a given patient if that patient experiences a threshold or higher toxicity at 3 fractions per week.
- Acute toxicities will be scored from the start of treatment through 90 days post completion of radiation therapy. Late radiation toxicities will be scored from 90 days post completion of radiation therapy.

5.4 Target volume and rectal dose limits.

Target volume. The GTV will generally be defined to include the entire prostate gland as visualized on CT scan. Seminal vesicles will be included in the GTV for 75% of the prescription dose if the estimated risk for seminal vesicle involvement is $\geq 15\%$ (24). For situations where there is less than 15% risk of seminal vesicle involvement, the base of the seminal vesicles may be included in the GTV at the discretion of the treating physician. The CTV will represent the same volume as the GTV plus a 0.3 cm margin in all dimensions except at the prostate-rectal interface, for which a margin of between 0 and 0.3 cm can be used. The PTV will include the CTV with a margin to account for patient and organ motion. This margin beyond the CTV is expected to range between 0 – 0.4 cm depending upon the accuracy of the daily pretreatment localization method used. Some form of pretreatment prostate localization must be used, either transabdominal ultrasound, Megavoltage CT (using Tomotherapy) or fiducial markers. Block margins will be chosen to provide adequate coverage of the PTV with no more than 10% dose heterogeneity across the PTV. At least 95% of the PTV must receive the prescription dose or higher. All planning will be carried out using an intensity modulated radiation therapy treatment planning system and delivered with an IMRT capable LINAC or with the tomotherapy machine.

Rectal dose limits. The rectal wall volume (outer minus inner) will be contoured for a total length of 11-12 cm beginning at approximately the inferior-most portion of the ischial tuberosities and extending to at least one cm above the most cranial extent of the treatment fields. Rectal wall percent volumes versus dose, as derived from the dose volume histogram, should be kept at or below values given in Table 2 whenever possible:

Table 2: Rectal Percent Limits vs. Dose

Level	Dose per Fx (Gy)	# Fxs	Total dose (Gy)	Dose (Gy)					
				30	35	40	50	55	60
I	2.94	22	64.68	-	-	37%	25%	-	13.5 %
II	3.63	16	58.08	-	38%	32%	19%	12%	-

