5.6 Adverse Effects

5.6.1 Acute toxicity

Acute toxicities will be scored from the start of radiation to 90 days after completion of radiation. Early urinary and GI toxicity will be used to determine the number of fractions deliverable per week as described in Section 5.2. Toxicity grading will be based on a modified RTOG grading criteria (25) (see below).

	Grade 1	Grade 2*	Grade 3	Grade 4
Acute GU	Requiring no medication	Frequency of urination or nocturia, which is less frequent than every hour, dysuria, urgency, bladder spasm requiring local anesthetic. New obstructive symptoms requiring an alpha blocker	Frequency with urgency and nocturia hourly or more frequently/dysuria, pelvis pain or bladder spasm requiring frequent narcotic; gross hematuria with or without clot formation.	Hematuria requiring transfusion; acute bladder obstruction not secondary to clot passage, ulceration, or necrosis
Acute GI	Requiring no medication	Diarrhea requiring parasympatholytic drugs; mucous discharge not necessitating sanitary pads; rectal or abdominal pain requiring narcotic analgesics.	Diarrhea requiring parenteral support; severe mucous discharge necessitating sanitary pads, abdominal distension.	Acute or sub-acute obstruction, fistula or perforation; GI bleeding requiring transfusion; abdominal pain or tenesmus, requiring tube decompression or bowel diversion

* The pre-existing use of an alpha blocker for GU symptoms or of an antidiarrheal agent for GI symptoms does not constitute a Grade 2 toxicity

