5.6.3 Serious Adverse Events

Serious adverse events (SAE) will be defined as all Grade 4 and Grade 5 toxicity. SAE'S will be phoned in to the Study Chairman at [contact] within one working day of the event. SAE's will be reported by the UW data managers to the DSMB and the Clinical Trials Monitoring Committee administrator within one business day of notification of SAE. These will also be discussed at regularly scheduled Disease Oriented Working Group meetings.

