5.8 Duration of Therapy

Study treatment will be stopped if:

- The patient refuses the study treatment
- The patient's physician feels that continuing the study treatments would not be in the patient's best interest.
- The patient experiences severe treatment related toxicities as outlined in section 5.6.3.
- There is clear evidence of progressive disease.
- Treatment interruption more than 2 weeks.

All patients will be followed for disease status until progression and for survival until death.

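### For treatment-related grade 4 acute toxicity during the radiation course, section 5.3 says pause a week and resume, section 5.8 says stop, and nothing says which governs

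*Combined protocol and SAP*

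**What the plan says.** **Section 5.3, individual-patient rule.** The trigger is open-ended upward: "For an individual patient who develops acute toxicity at or above the Grade 3 level". The action is "that patient will be placed on treatment break for one week and treatments will then resume at the next lower treatment frequency". The worked example, a patient on four fractions a week, uses the same open range: "at the time grade 3 or higher acute toxicities developed, he would subsequently be treated 3 times per week". The treating physician may prescribe a longer break; stopping is not mentioned. A later bullet allows a patient who reaches threshold toxicity or worse on three fractions a week to drop to two, which again assumes that treatment goes on.

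**Acute grade 4 events.** Section 5.3 states the scoring window: "Acute toxicities will be scored from the start of treatment through 90 days post completion of radiation therapy". It opens with the first fraction, so acute grade 4 events can fall within the course. The table in 5.6.1 defines them for both GU and GI; the GI entry begins "Acute or sub-acute obstruction, fistula or perforation; GI bleeding requiring transfusion".

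**Sections 5.8 and 5.6.3.** Section 5.8 opens its list with "Study treatment will be stopped if". One item is: "The patient experiences severe treatment related toxicities as outlined in section 5.6.3". Section 5.6.3 outlines one set of events: "Serious adverse events (SAE) will be defined as all Grade 4 and Grade 5 toxicity". It makes no exception for acute events. Other items in 5.8 are a physician's judgement that continuing is not in the patient's interest, and a treatment interruption of more than two weeks.

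**The concern.** Both rules are mandatory, and both apply to the same patient: one with a treatment-related grade 4 acute event who still has fractions to receive. Under 5.3 he resumes after a week at a lower weekly frequency; under 5.8 he receives no more study treatment. Neither section refers to the other.

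Patient safety and consistent handling are at stake. Read literally, 5.3 restarts pelvic radiation one week after an event as serious as a perforation. Other grade 4 events, such as acute bladder obstruction or haematuria needing transfusion, are ones on which reasonable clinicians could differ, so the four institutions listed at the front of the protocol could treat similar patients in opposite ways. One reading continues radiation after a grade 4 event; the other ends a potentially curative course. The protocol should make that choice once.

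**Working it through.** The plan states no figure here to reproduce. The check sets the rules side by side and then sizes the difference between them.

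**Step 1. Grade by grade, treatment-related acute toxicity before the last fraction**

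| Grade | Section 5.3, individual rule | Section 5.8 with 5.6.3 | Result |
|---|---|---|---|
| 3 | One-week break, resume at lower frequency | Not triggered | No conflict |
| 4 | One-week break, resume at lower frequency | Stop study treatment | Direct conflict |
| 5 | Moot (fatal) | Moot | No practical conflict |

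After the last fraction there is nothing left to resume or stop, so grade 4 events in the following 90 days are outside the conflict, although they are still scored as acute.

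**Step 2. Does any other provision settle it?**

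- The two-week interruption limit in 5.8 does not, because the 5.3 break is one week.
- The longer break in 5.3 is optional. It leads to a stop only if it exceeds two weeks, and then through the interruption item, not the toxicity item.
- The physician's-judgement item in 5.8 is a separate ground for stopping. It does not make the toxicity item optional, and it does not limit 5.3.
- The reporting duties (a call to the Study Chair within one working day in 5.6.3, DSMB notice within 24 hours in 8.4) give no rule for the individual patient.

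**Step 3. Size of the difference per case**

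Inputs from Table 1 in section 5.2: 22 fractions of 2.94 Gy (Level I), 16 of 3.63 Gy (Level II), 12 of 4.3 Gy (Level III).

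The conflict can arise at any time in the course. Course length is fractions divided by fractions per week; at four a week this is 22/4 = 5.5, 16/4 = 4.0 and 12/4 = 3.0 weeks.

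Further dose under 5.3 = fractions remaining × dose per fraction. Further dose under 5.8 = 0. The timing of the event is an assumption.

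| Event timing (assumed) | Fractions remaining × dose | Further dose under 5.3 |
|---|---|---|
| Level I, mid-course | 11 × 2.94 | 32.34 Gy |
| Level II, mid-course | 8 × 3.63 | 29.04 Gy |
| Level III, mid-course | 6 × 4.3 | 25.80 Gy |
| Level I, after 6 of 22 (about one quarter given) | 16 × 2.94 | 47.04 Gy |
| Level III, after 9 of 12 (three quarters given) | 3 × 4.3 | 12.90 Gy |

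Between roughly one quarter and three quarters of the way through, the difference runs from 12.9 to 47.0 Gy across the three levels.

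**The case against.** The strongest reply is that the sections can be read together. Section 5.3 adjusts weekly frequency for a patient who remains on treatment, and 5.8 lists the reasons for leaving treatment. The 5.3 rule also makes no exception for refusal or progressive disease, yet nobody would see a conflict with 5.8 there. Section 5.8 is also the narrower toxicity rule, so the natural reading is that grade 3 means pause and reduce, and grade 4 means stop. On this view only a cross-reference is missing.

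The safety scenario can also be called remote. Both rules begin by halting radiation and part only after about a week. By then the Study Chair and the DSMB should know of the event, and the physician can extend the break or stop. The Gy figures are simply the undelivered dose at assumed times and say nothing about likelihood.

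Much of this stands. The reading in which 5.8 overrides is sensible, and the fix below adopts it. The safeguards do lower the risk, and the dose figures measure the consequence of a case, not its probability. But the precedence is stated nowhere. A site could equally take 5.3 as governing, since it deals specifically with acute toxicity on treatment, and its example repeats the open-ended grade range. Refusal and progression are not triggers named in 5.3; grade 4 acute toxicity falls within its stated trigger. The 5.3 instruction is therefore wrong as written for grade 4, not merely short of detail.

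Whether every on-treatment grade 4 event should end a curative course is a fair clinical question. It is a reason for the sponsor to state one rule, not for leaving two.

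**Conclusion.** The concern holds and should be fixed. For treatment-related grade 4 acute toxicity arising before the end of radiation, the protocol gives two opposite mandatory instructions and no order of precedence. This rests on the text alone and confidence is high.

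Per case, the instructions differ by all the dose not yet given: about 26 to 32 Gy at mid-course, depending on level, and 12.9 to 47.0 Gy over the wider range of timings. Those figures depend on the assumed timing and on the rest of the planned course being delivered after resumption. How often this would happen cannot be said, because the documents give no rate of on-treatment grade 4 events. No effect is claimed on the late-toxicity rate, the escalation decisions or any statistical quantity in section 8.

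**What to change.** In the individual-patient bullet of 5.3, limit both the trigger and the worked example to grade 3. Then add a sentence such as: *Treatment-related grade 4 acute toxicity during treatment is handled under 5.8 (study treatment stopped).*

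Leave the group rules in 5.3 as they are: they count grade 3 or higher to set treatment frequency for later patients and are not part of this conflict.

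Two optional clarifications would help. Make the option of a longer break subject to the two-week limit in 5.8, and put the same grade 3 limit on the bullet allowing two fractions a week. If the sponsor wants some grade 4 events to permit resumption, 5.8 should name them; the essential point is a single stated rule.

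The cost is a wording amendment, essentially to one bullet of 5.3. Sample size, dose levels and analysis do not change.
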